9.6.1.1. Primary Efficacy Analysis

The primary efficacy variable, change from baseline to week 4 in the weekly average of the daily average NRS scores, will be analyzed using a Mixed Model Repeated Measures (MMRM) model with change from baseline in the weekly average of the daily average NRS scores at weeks 2 and

4 as the dependent variable; visit in weeks, treatment, and treatment by visit interaction as fixed factors; baseline weekly average of the daily average NRS scores as covariate; and patient as random effect. The unstructured covariance matrix for repeated observations within patients will be used. The primary treatment comparison will be conducted at week 4 in this model. All tests will be 2-sided at a significance level of 0.05. More details will be provided in the Statistical Analysis Plan.

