## **2.3. Sample Size and Power Considerations**

In prior studies of gabapentin or pregabalin treatment of PHN, the difference in mean pain scores between active- and placebo-treated groups ranged from 1.0 to 1.3. For this study, a conservative estimate of 1.0 will be used. Assuming a standard deviation of 2.35, a sample size of 88 per arm (a total of 264 patients) would be needed to provide 80% power with a 2-sided test at 5% significance level to detect a 1.0-point difference. Assuming an approximately 20% dropout rate, 110 patients per arm (a total of 330 patients) will be randomly assigned to each treatment group.

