## **2.4. Randomization and Blinding**

This is a randomized, double-blind, placebo-controlled study. All tubes of study drug will be identical, and the ointments will be indistinguishable. Patients, investigators, and all clinical study center staff will remain blinded to treatment assignment during the study. Eligible patients will be randomly assigned via interactive-response technology (IRT) in a 1:1:1 ratio to 4% w/w TV-45070 ointment, 8% w/w TV-45070 ointment, or placebo ointment. Randomization will be stratified by the R1150W underlying genotype in the SCN9A gene: homozygous minor allele (positive, AA), heterozygous (positive, AG), and homozygous common allele (negative, GG).

In addition, the Sponsor's clinical personnel involved in the study will be blinded to the study drug identity until the database is locked for analysis and the treatment assignment revealed. A statistician not assigned to the study will be responsible for the randomization code, and the final randomization code will be maintained by the service provider.

Patients will be randomly assigned to treatment through a qualified randomization service provider (eg, IRT). This system will be used to ensure a balance across treatment groups; no effort will be made to maintain a balance among treatment groups within a study center.

The clinical study center will receive study drug kits, and kits will be assigned to individual patients by the IRT system based on the patients' randomization assignments. The IRT system will record the kit numbers for all patients. Designated study center staff, who will remain blinded to the treatment assignments, will dispense the kits to patients based on the kit numbers

assigned to patients by the IRT system. In case of emergency, the investigator and designated study center staff can call the IRT system to unblind the treatment for a specific patient.

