#### 6.2.2. Primary Analysis

The primary efficacy variable for this study is the change from baseline to week 4 in the weekly average of the daily average NRS pain scores. This variable will be analyzed using a Mixed Model Repeated Measures (MMRM) model with change from baseline in the weekly average of the daily average NRS scores at weeks 1, 2, 3 and 4 as the dependent variable; week, pooled study center, treatment, and treatment by visit interaction as fixed factors, baseline weekly average of the daily average NRS scores as covariate; and patient as a random effect. The unstructured covariance matrix for repeated observations within patients will be used. If the model does not converge, the maximum-likelihood (ML) estimation method will be used instead of the default restricted ML (REML) method. If the model still does not converge, then simpler covariance structures with less parameters will be used in the following order until the model does converge: heterogeneous autoregressive (1) (ARH[1]); heterogeneous compound symmetry (CSH); autoregressive (1) (AR[1]); and compound symmetry (CS). The primary treatment comparison will be conducted at week 4 in this model.

The least square (LS) means and standard error of each treatment group, LS means differences including standard error, 95% confident interval (CI) and p-values, between each active group and the placebo group for the change from baseline to weeks 1, 2, 3 and 4 in the weekly average of the daily average NRS pain scores will be presented in the tables.

SAS code for primary endpoint:

```

Proc mixed data=datain;
Class treatment week patient;
Model change=base treatment center week treatment*week/ddfm=kr;
Repeated week/sub=patient type=un;
Lsmean treatment*week/pdiff cl ;
*** treatment order in the data will be placebo, 4%, 8%*****;

Estimate '4% vs. Placebo at week 4' treatment -1 1 0 treatment*week 0 0 0 -1
0 0 0 1 0 0 0 0/ cl;
Estimate '8% vs. Placebo at week 4' treatment -1 0 1 treatment*week 0 0 0 -1
0 0 0 0 0 0 1/cl;

Run;

```

A descriptive summary of the weekly average of the daily average NRS pain scores at baseline, weeks 1, 2, 3 and 4, as well as the change from baseline will be provided by treatment group.

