### 6.2.3. Sensitivity Analysis

Two sensitivity analyses will be performed in order to assess the robustness of the results of the primary analysis to changes in the assumptions and data characteristics. The first sensitivity analysis is a multiple imputation method to handle missing weekly average of the daily average NRS pain scores for week 4. Consistent with the recommendations of the National Academy of Sciences report (National Research Council 2010), under the assumption of missing at random (MAR) and taking into account of potential bias towards the active arm for patients who withdrew from the study due to adverse events, the following steps will be carried out in SAS using the MI, Mixed, and MIANALYZE procedures:

- Step 1: prepare data set for MI procedure (PROC MI)

The following auxiliary variables are to be included in the model for PROC MI:

- Treatment (1=placebo, 2=TV45070 4%, 3=TV45070 8%)
- R1150W genotype (1=AA, 2=GA, 3=GG)
- All observed pain scores, screening, baseline, and weekly averages at each post randomization week (week 1, week 2, week 3, week 4)

The treatment will be coded to 1 (placebo) for those in the active arms withdrawn from study due to an adverse event or lack of efficacy. Thus, the missing week 4 pain scores will be imputed based on the observed placebo patient's data. In order to adjust for the use of rescue medication at week 4, the average weekly pain intensity at week 4 will be set to missing for patients who used an excessive amount of rescue medication during the week before the multiple imputation. Excessive use of rescue medication is defined as the use of rescue medication on at least 4 out of 7 days of the week 4 treatment.

- Step 2: run PROC MI. The following SAS code may be used to generate the imputed data sets:

```

Proc mi data=datain nimpute=5 seed=598719001 out=mi_out
  Maximum=10 minimum=0 round=0.01;
  Class treat genotype;
  Var treat genotype screening baseline week1 week2 week3 week4;
  Monotone reg;

```

Run;

Note: if the missing data pattern is not monotonic, a Markov Chain Monte Carlo (MCMC) method will be used instead of a regression method for imputing missing data. R1150W genotype will be used, with all 3 possible categories.

- Step 3: run mixed procedure (PROC MIXED) using the data from PROC MI

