The output data set MI\_OUT, from the above MI procedure, will contain 5 complete data sets with the missing data points filled using the specified imputation methods, and 1 additional variable, \_IMPUTATION\_, to indicate the order of the imputed data sets. Then within each data set, the primary variable, change from baseline at week 4, will be derived by subtracting baseline from week 4. Each data set will be analyzed using the ANCOVA model with the primary variable and the dependent variables, the screening and baseline scores as covariates, pooled study center, treatment and genotype as factors in the model. The following SAS code may be used to analyze the imputed data sets.

```
ODS output diffss=mixed_out;
Proc mixed data=mi_out method=reml;
  By _imputation_;
  Class center armcd genotype;
  Model change4 = center armcd genotype baseline screening;
  Lsmeans armcd/diff;
Run;
```

ARMCD represents the treatment the patient was randomized to receive.

- Step 4: calculate overall p-value and construct 95% confidence interval for the treatment difference.

The output data from the above SAS code will contain the estimate of the mean difference and the standard error of the estimate from each of the 5 data sets. The SAS procedure mianalyze (PROC MIANALYZE) will be used to generate an overall p-value and 95% confidence interval for the treatment difference. The following SAS code may be used.

```
ODS output parameterestimates=parmest;
Proc mianalyze data=mixed_out alpha=0.05 theta0=0;
  Model effects estimate;
  Stderr stderr;
Run;
```

The second sensitivity analysis will be similar to the first one except that the baseline observation carried forward (BOCF) method will be used to impute the missing week 4 weekly average of the daily average NRS pain scores for those who discontinued the study early due to adverse event or lack of efficacy. Details for the week 4 imputation methods for missing weekly average of the daily average NRS pain scores for the two sensitivity analyses are given in [Table 2](#) below.

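### The primary and secondary linear models leave out R1150W genotype, the only factor the randomization is stratified by: minor, and nearly free to correct

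*SAP*

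**What the plan says.** - **Randomization.** SAP 2.4: "Randomization will be stratified by the R1150W underlying genotype in the SCN9A gene", with three levels (AA, AG, GG). No other factor is named, and balancing within centers is expressly not attempted. On balance overall: "This system will be used to ensure a balance across treatment groups". No block size is given.
- **Primary model.** The factors in SAP 6.2.2 are "week, pooled study center, treatment, and treatment by visit interaction as fixed factors", with baseline NRS as covariate. The code agrees: "Model change=base treatment center week treatment*week/ddfm=kr". Protocol 9.6.1.1 has "visit in weeks, treatment, and treatment by visit interaction as fixed factors" and no genotype either.
- **Secondary linear models.** SAP 6.3.2 analyses the continuous secondary endpoints in the same way as the primary. The PGIC MMRM and the NePIQoL ANCOVA are written out separately, also without genotype.
- **Sensitivity analyses.** SAP 6.2.3 puts genotype in the imputation model ("R1150W genotype will be used, with all 3 possible categories") and in the ANCOVA: "Model change4 = center armcd genotype baseline screening". The results go to Table 15.2.1.3.
- **Reason.** None is visible, and SAP section 10 does not mention genotype. The exploratory sections are redacted and may hold other genotype analyses, but these would not change the model in 6.2.2.

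**The concern.** When allocation is balanced within strata and the stratification factor predicts outcome, the arm means vary less from trial to trial than a model without that factor assumes. The reported standard error is then too large. The treatment estimate is not biased and type I error is not inflated; the test falls a little below its nominal 5% and gives up some power.

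The plan is also uneven. It adjusts for pooled center, which the randomization does not balance, and leaves out genotype, which it does. The sensitivity analyses change both the missing-data handling and the covariate set, so a gap between Table 15.2.1.3 and the primary result could not be put down to missing data alone.

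Protocol 1.3.2.3 gives some reason to expect a relationship: the polymorphism may alter pain perception, and carriers in the earlier PHN study tended to respond less to placebo. That finding was not significant, concerned response rates, and gives no size for NRS change.

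**Working it through.** **Inputs from the documents.** Treatment difference 1.0, SD 2.35, two-sided 5%, 88 completers per arm (SAP 2.3). On dropout: "Assuming an approximately 20% dropout rate, 110 patients per arm". Carrier rate p = 9/52 = 0.173 (Protocol 1.3.2.3).

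**Assumed.** A carrier-versus-GG shift d in mean NRS change, the same in every arm and for AA and AG; blocks of 6 within stratum; random dropout.

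**1. The plan's own figure.** A two-sample t-test with difference 1.0 and SD 2.35 has power 79.7% at 87 per arm and 80.2% at 88, and 88/0.8 = 110. Both planned numbers reproduce.

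**2. Closed form, week 4 only.** The share of variance due to genotype is f = p(1−p)d²/SD² = 0.1431 d²/5.5225. If a random fraction q of patients drops out and contributes nothing, balance among those left is partly lost, and the actual alpha is 2·(1 − Φ(1.96/√(1 − (1−q)f))).

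For d = 1.0 and q = 0.2: f = 0.0259, (1−q)f = 0.0207, √(1 − 0.0207) = 0.9896, 1.96/0.9896 = 1.981, alpha = 0.0476.

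With SE = 2.35·√(2/88) = 0.3543, power without genotype is Φ((1 − 1.96·0.3543)/(0.3543·0.9896)) = 80.8%. With genotype it is Φ(1/(0.3543·√(1 − 0.0259)) − 1.96) = 81.6%.

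| d | f | alpha, no dropout | alpha, q = 0.2 | power points lost, q = 0.2 |
|---|---|---|---|---|
| 0 | 0 | 0.050 | 0.050 | 0 |
| 0.5 | 0.6% | 0.0493 | 0.0494 | 0.2 |
| 1.0 | 2.6% | 0.0470 | 0.0476 | 0.8 |
| 2.0 | 10.4% | 0.0384 | 0.0407 | 3.0 |

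The exact 95% interval for 9/52 is 8.2% to 30.3%. Over it, d = 1.0 gives alpha 0.049 to 0.047 and 0.4 to 1.1 power points.

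**3. Four-week unstructured MMRM, simulated.** 330 patients, 20% monotone dropout spread over the four weeks, within-patient correlation 0.7 (assumed), baseline covariate, no center term, 1,500 runs per row. Dropouts' earlier weeks count here, so power starts higher.

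| d | SE too wide by* | alpha | power without / with genotype |
|---|---|---|---|
| 0.5 | 0.3% | 0.049 | 84.1% / 84.3% |
| 1.0 | 1.2% | 0.047 | 84.4% / 85.0% |
| 2.0 | 5.4% | 0.039 | 85.6% / 87.8% |

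*Reported SE against the actual SD of the estimate; alpha and power follow from that ratio.

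If the shift grows linearly to week 4, alpha is 0.049, 0.047 and 0.040, and a genotype main effect regains 0.2, 0.5 and 2.0 power points.

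**4. Direct rejection counts.** Week 4 only, blocks of 6 plus dropout, 20,000 null runs, Monte Carlo SE 0.0015. Without/with genotype: 0.0500/0.0524 at d = 1 and 0.0430/0.0516 at d = 2. With no balance within strata: 0.0500/0.0493 and 0.0515/0.0499, so the conservatism disappears. Adjusting still gains about 1.0 power point at d = 1 in that case (closed form).

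**5. How many AA patients?** Under Hardy-Weinberg proportions (assumed), the minor-allele frequency is 1 − √(1 − 0.173) = 0.0906. Expected AA is 330 × 0.0906² = 2.7, or 0.6 to 9.0 over the interval for p. A three-level factor would have a nearly empty level.

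**The case against.** The strongest case against is that nothing material follows. There is no bias and no inflation, and for shifts of 0.5 to 1.0 point the loss is a fraction of a power point. The larger figures need a 2-point shift, twice the planned treatment difference, which nothing in the documents supports. This stands, and it is why the point is graded minor.

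At d = 1 the rejection rate without genotype (0.0500) cannot be told apart from 5%. This also stands as far as it goes. However, the gap between the two models on the same data, 0.0524 − 0.0500 = 0.0024, is the size the closed form predicts (0.0500 − 0.0476). The effect is clear at d = 2.

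The earlier study hints at effect modification rather than a common shift: heterozygotes responded more to TV-45070 and carriers less to placebo, neither significantly. If carriers shift by +d in both active arms and −d on placebo, the average shift is (d + d − d)/3 = d/3, and a genotype main effect gains only about 0.1 power point at d = 1 and 0.4 at d = 2. That weakens the power argument but leaves the null calculation alone.

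The block size is unknown and the simulation used two strata and no center term, so the conservatism is conditional. Finally, a genotype-adjusted week-4 estimate will appear in Table 15.2.1.3. It will, but the primary p-value still comes from the model without genotype.

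**Conclusion.** The concern holds, as a minor one. The sole stratification factor is missing from the primary and secondary linear models and present in the sensitivity model, with no reason visible.

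For shifts up to 1 point the actual alpha is about 0.047 to 0.049 and the power loss is under one point at the observed carrier rate. The 2-point rows mark an extreme, not an expectation. The size rests on an assumed common carrier shift, on 9/52 as the carrier rate and, for the conservatism, on balance within strata. With no genotype effect nothing is lost. The primary test remains valid as written; the change is a small improvement and removes an inconsistency.

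**What to change.** Before unblinding:

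1. Add genotype as a fixed factor to the primary MMRM (text, CLASS and MODEL statements), the secondary and PGIC MMRMs, and the NePIQoL ANCOVA.
2. State a numeric pooling rule applied to blinded genotype counts in the FAS. For example, pool AA with AG if there are fewer than 15 AA patients over all arms (under 5 per arm on average); otherwise keep three levels. The 15 is a proposal, and any number fixed in advance serves. Under Hardy-Weinberg the chance of fewer than 15 is above 99.9% at 9/52 and 96% at the upper limit, so pooling is very likely. Use the same coding in PROC MI and the sensitivity ANCOVA, replacing the three-category instruction in SAP 6.2.3.
3. Record the addition in SAP section 10, since the model would then differ from Protocol 9.6.1.1.

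Optional: align the screening-score covariate between the primary and sensitivity models, add genotype-by-week, and add genotype to the responder logistic models.

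The cost is SAP wording and one variable already held for randomization: 1 degree of freedom if AA and AG are pooled, 2 if not. Conduct and sample size do not change. If genotype is left out on purpose, one sentence in 6.2.2 giving the reason is enough.

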## 6. EFFICACY ANALYSIS

### 6.1. General

The FAS will be used as the primary analysis for all efficacy analyses. The PP population will be supportive for efficacy analyses. All statistical testing will be carried out using 2-tailed tests at the 5% level of significance. Summaries will be presented by treatment group as randomized/assigned unless specified otherwise.

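### The last-resort AR(1) and CS fits in the primary model's fallback use model-based errors that can be too small at week 4 if variance rises over the weeks

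*SAP*

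**What the plan says.** SAP 6.2.2 models the change from baseline at weeks 1 to 4 and tests each active arm against placebo at week 4. The text specifies "patient as a random effect. The unstructured covariance matrix for repeated observations within patients will be used". The program beneath it has no RANDOM statement; its covariance is set by "Repeated week/sub=patient type=un" alone, with Kenward-Roger degrees of freedom and no EMPIRICAL option.

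The fallback starts with a change of estimation method: "If the model does not converge, the maximum-likelihood (ML) estimation method will be used instead of the default restricted ML (REML) method". If that fails, simpler covariance structures are tried until one converges. Heterogeneous AR(1) comes first, and the list continues with "heterogeneous compound symmetry (CSH); autoregressive (1) (AR[1]); and compound symmetry (CS").

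The text does not say whether the simpler structures return to REML or stay with ML, and it does not ask for a robust standard error at any step. SAP 6.3.2 analyses most continuous secondary endpoints, and PGIC, in a similar way to the primary.

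**The concern.** Two steps of the fallback sit badly with a test made at one visit.

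- **ML.** The unstructured matrix for four weeks has 4 × 5 / 2 = 10 parameters under ML just as under REML, so the switch simplifies nothing. ML also takes no account of the mean parameters that have been estimated, so its variances are biased downward.
- **AR(1) and CS.** Each uses one variance for all four weeks. The primary contrast is at week 4, so its standard error would come from the average variance over weeks 1 to 4. If the spread of change grows during treatment, that average is below the week 4 variance. Kenward-Roger does not repair a wrong covariance structure.

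The text also disagrees with the program. A patient random effect on top of an unstructured matrix makes 11 variance parameters for 10 identifiable quantities, and ML cannot cure that.

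At stake are the primary p-values and confidence intervals, if these steps are ever used.

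**Working it through.** **Inputs from the SAP.** Section 6.1: "All statistical testing will be carried out using 2-tailed tests at the 5% level of significance". Section 2.3: on the size, "Assuming a standard deviation of 2.35, a sample size of 88 per arm (a total of 264 patients"), with a power target of 80%; on the effect, "a conservative estimate of 1.0 will be used". Section 2.3 also gives 20% dropout and 110 randomized per arm, and section 4.6 about 15 pooled centers. The documents give no weekly SDs or correlations; those below are assumptions, with week 4 fixed at 2.35.

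**The plan's own figure.** n per arm = 2 × (1.960 + 0.842)² × 2.35² / 1.0² = 86.7, so 87 by the normal approximation. With the t distribution, power is 79.7% at 87 and 80.2% at 88, so 88 reproduces. 88 / 0.8 = 110 per arm, 330 in total.

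**ML step, closed form.** SE ratio = √((N − p)/N); type I error = 2 × (1 − Φ(1.96 × ratio)).
- p = 3 (treatment means only), N = 264: ratio 0.994, error 5.1%.
- p = 18 (adding baseline and 14 center contrasts), N = 264: ratio 0.965, error 5.9%. This is an upper end, because baseline and center have no interaction with week and are shared over four weeks.

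**AR(1) or CS, closed form with complete data.** SE ratio = √(mean of the four weekly variances) / 2.35. For SDs 1.7, 2.0, 2.2, 2.35: (2.89 + 4.00 + 4.84 + 5.5225)/4 = 4.313; √4.313 = 2.077; 2.077/2.35 = 0.8837. Then 1.96 × 0.8837 = 1.732, and the error is 8.3%.

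**Simulation under the null.** Six scenarios (two with constant SD) of 2000 datasets each: 330 patients, 15 centers, about 21% monotone dropout at random, the SAP's mean model, and model-based Wald t tests of both contrasts at week 4. That gives 4000 tests per cell, Monte Carlo SE about 0.4 points.

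| Assumed SDs, weeks 1–4 | SE ratio (closed form) | Type I error (closed form) | AR(1)/CS, REML | AR(1)/CS, ML |
|---|---|---|---|---|
| 2.35 throughout | 1.0000 | 5.0% | 4.6–6.1% | 5.0–6.9% |
| 2.0, 2.15, 2.25, 2.35 | 0.9325 | 6.8% | 7.4–7.6% | 8.0–8.6% |
| 1.7, 2.0, 2.2, 2.35 | 0.8837 | 8.3% | 8.9–9.1% | 9.8–10.2% |
| 1.4, 1.9, 2.15, 2.35 | 0.8434 | 9.8% | 10.6–10.9% | 11.7–12.2% |
| 2.6, 2.5, 2.4, 2.35 | 1.0487 | 4.0% | 4.4–4.9% | 5.1% |

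Over all six scenarios:
- Unstructured, ARH(1) and CSH by REML: 4.4–5.6%.
- Unstructured by ML: 4.6–6.3%, which is 0.2–0.7 points above unstructured by REML.
- Unstructured fits converged in 100.0% of datasets (rounded), with an optimizer other than SAS and without a patient random effect.

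**Sandwich error.** This was tried only in a small null simulation of 300 tests per cell, at a moderate SD rise. AR(1) and CS gave about 10–11% with model-based errors and about 6–7% with the sandwich; unstructured and ARH(1) by REML were near 6%. The Monte Carlo SE there is √(0.06 × 0.94/300), about 1.4 points, so it shows direction only.

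**The case against.** The strongest reply is that the SAP already puts the protective structures first. A reader might infer that the plan goes from ML straight to a common variance. It does not: ARH(1) and CSH come in between, so AR(1) is reached only after unstructured by REML, unstructured by ML, ARH(1) and CSH have all failed. That stands.

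A reader might also infer that the fallback necessarily inflates the type I error. The documents do not support that either. They give a single SD, and inflation needs a week 4 variance above the average of weeks 1 to 4. Protocol 5.4 allows rescue acetaminophen during treatment except in the final week, so equal variance should not be presumed, but this does not fix the direction.

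Third, the random-effect wording might seem to make failure likely. If the SAP's program is run, that effect is not fitted; what remains is a mismatch between text and code.

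Trying ML before giving up the unstructured matrix is also defensible, since it leaves the week 4 variance free. And the two sensitivity analyses in SAP 6.2.3 are week 4 ANCOVAs by REML. They address missing data, but do not depend on the fallback structure and could expose an artefact.

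For secondary endpoints measured only at weeks 2 and 4, ARH(1) and CSH have three parameters, as many as the unstructured matrix, so they are hardly a fallback. But failure of a three-parameter matrix is even less plausible.

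What survives is narrow: when AR(1) or CS is used, nothing in the rule protects the week 4 standard error.

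**Conclusion.** The point holds as a minor, contingent defect in the rule. By REML, AR(1) or CS gives a week 4 type I error of about 7–11% if the weekly SD rises to 2.35 from an assumed 2.0 to 1.4 at week 1, and little or no inflation if the SD is constant or falling. If ML were carried into those fits, which the text leaves open, the rising-SD range would be about 8–12%. The ML step on the unstructured model is worth well under one point, and ARH(1) and CSH by REML hold the level.

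These sizes rest on assumed weekly SDs, correlations and dropout. The chance of reaching AR(1) is very small with four visits and about 330 patients.

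**What to change.** In SAP 6.2.2, before unblinding:

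- Keep REML throughout. Replace the ML step with a retry of the unstructured fit using Fisher scoring or other starting values.
- Keep the heterogeneous structures ahead of AR(1) and CS.
- Require an empirical (sandwich) standard error, with a stated degrees-of-freedom method, for any structure other than unstructured, and at least for AR(1) and CS if they stay. Deleting those two is optional; without them the plan has no prespecified last resort.
- Remove the patient random effect from the text so that it matches the program, and do the same for PGIC in SAP 6.3.2.

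The cost is a few lines of text and one PROC MIXED option. Kenward-Roger degrees of freedom are given up in the fallback fits, which matters little at about 300 patients. The sandwich error corrects the standard error only; it does not remove any bias in the estimate from a wrong covariance under dropout, which is a further reason to keep AR(1) and CS last.

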#### **4.6. Center**

The trial will be conducted in approximately 55 study centers in the United States. In order to include center into the model, centers will need to be combined to create approximately 15 big centers. Centers may be pooled according to the number of patients enrolled at each site by keeping the largest sites intact and pooling the remainder of the larger sites with smaller sites to form pooled sites. A final plan for pooling will be made and documented in Statistical Data Review meeting minutes prior to unblinding. The pooled centers will be used in the efficacy analyses as appropriate.

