### 6.3.2. Secondary Efficacy Analysis

The above secondary efficacy variables will be analyzed in the similar way as the primary analysis for the primary efficacy variable.

- Change from baseline to weeks 1, 2, 3 and 4 in the weekly average of the average pain score recorded in the evening
- Change from baseline to weeks 1, 2, 3 and 4 in the weekly average of the average pain score recorded in the morning

- Change from baseline to weeks 1, 2, 3 and 4 in the weekly average of the worst pain score recorded in the evening (worst pain is defined as the patient-reported worst pain intensity over the prior 24 hours)
- Change from baseline (randomization visit) to weeks 2 and 4 in the NPSI score
- Change from baseline (randomization visit) in DSIS scores at weeks 2 and 4
- Change from baseline (randomization visit) to weeks 2 and 4 in maximal intensity of patients' brush-evoked allodynia, as measured on the 11-point NRS
- Change from baseline (randomization visit) to weeks 2 and 4 in maximal intensity of patients' punctate-evoked hyperalgesia using a Medipin, as measured on the 11-point NRS

In addition, the following analyses will be done:

[figure not shown]
- Percentage of patients with  $\geq 30\%$  improvement and  $\geq 50\%$  improvement from baseline in the weekly average of the daily average NRS scores at week 4 will be analyzed using logistic regression model with pooled study center, treatment as fixed factors and baseline NRS scores as covariate.
- Time to reach  $\geq 30\%$  sustained improvement from baseline in the weekly average of the daily average NRS scores will be summarized using Kaplan-Meier method.
- Patients' global assessment of treatment, as measured by PGIC scores, at weeks 2 and 4 will be analyzed using a MMRM model similar to the primary efficacy variable with pooled study center, week, treatment, and treatment by week interaction as fixed factors and patient as a random factor. The unstructured covariance matrix for repeated observations within patients will be used.
- Change from baseline (randomization visit) to week 4 in the NePIQoL score will be analyzed using an analysis of covariance (ANCOVA) model with pooled study center, treatment as fixed factors and baseline value as covariate. The missing week 4 values will be imputed using last observation carried forward (LOCF) method.

[figure not shown]
SAS code for ANCOVA model

[figure not shown]
```
Proc mixed data=datain order=data;
  Class center treatment;

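### The SAS program for the primary endpoint leaves center out of CLASS, although the SAP text makes pooled center a fixed factor

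*SAP*

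**What the plan says.** SAP 6.2.2 describes the primary model in words with "week, pooled study center, treatment, and treatment by visit interaction as fixed factors". The baseline pain score is the only covariate named. The program directly beneath declares "Class treatment week patient" and then specifies "Model change=base treatment center week treatment*week/ddfm=kr". Center is therefore in MODEL but not in CLASS.

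Three other places show how center is meant to enter:

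- SAP 4.6 says that "centers will need to be combined to create approximately 15 big centers" so that center can go into the model. It adds: "A final plan for pooling will be made and documented in Statistical Data Review meeting minutes prior to unblinding".
- The ANCOVA program for the imputed data in SAP 6.2.3 has "Class center armcd genotype".
- The NePIQoL ANCOVA program in SAP 6.3.2 has "Class center treatment".

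Neither document describes center as continuous. The protocol's own primary model (section 9.6.1.1) has no center term, so only the SAP can settle how center is handled.

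**The concern.** The text and the program of one section specify different models for the primary endpoint. What happens next depends on how center is coded, which the documents do not state. A character code stops PROC MIXED, and the slip is found at once. A numeric code lets it run without an error. The treatment differences would then be adjusted for a straight line through the center labels, and renumbering the pooled centers could change the primary p-value.

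The omission could also spread. SAP 6.3.2 analyses seven secondary variables in the manner of the primary analysis and uses a similar repeated-measures model for PGIC. A programmer who reuses the primary program would carry the error into those results.

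**Working it through.** **Inputs from the documents.** Difference 1.0, SD 2.35, 88 per arm, 20% dropout (SAP 2.3); three arms and four weeks (SAP 6.2.2); about 15 pooled centers (SAP 4.6); no balancing of treatment within center (SAP 2.4).

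**Assumed, because the documents do not give it.** Center explains 0 to 15% of the variance; the within-patient correlation is 0.8 (repeated-measures check only); data are complete.

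**1. The plan's own sample size.** n = 2(z₀.₉₇₅ + z₀.₈₀)²σ²/δ² = 2 × (1.960 + 0.842)² × 2.35² / 1.0² = 2 × 7.849 × 5.5225 = 86.7, so 87. With the noncentral t, power is 0.797 at 87 and 0.8015 at 88, so 88 per arm. Dropout: 88 / (1 − 0.20) = 110. Both figures reproduce, and neither uses center.

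**2. Model size.** Intercept 1 + baseline 1 + treatment 2 + week 3 + treatment by week 6 = 13 parameters.

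- As programmed, with a numeric code: 13 + 1 = 14.
- As described, with 15 centers as a factor: 13 + (15 − 1) = 27.

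The numerical ranks of the two design matrices are also 14 and 27.

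**3. Effect on the week-4 comparison.** Linear model with baseline, 3 × 88 patients, 15 centers assigned at random, 6000 simulated trials per setting:

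| Center share of variance | 0% | 2% | 5% | 10% | 15% |
|---|---|---|---|---|---|
| SE, slope / factor | 0.975 | 0.983 | 0.996 | 1.020 | 1.046 |
| Power at 1.0, factor | 0.780 | 0.785 | 0.795 | 0.826 | 0.833 |
| Power at 1.0, slope | 0.801 | 0.799 | 0.798 | 0.811 | 0.801 |
| Opposite verdicts at 1.0 | 5.3% | 6.3% | 7.7% | 7.9% | 9.1% |
| Opposite verdicts, no effect | 2.0% | 2.2% | 3.0% | 3.4% | 4.2% |

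Type I error is 0.045 to 0.056 (factor) and 0.049 to 0.055 (slope). The two estimates differ by at most 0.004 on average, with an SD of 0.08 to 0.15 NRS points.

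**4. Four-week repeated-measures model.** Unstructured covariance, 1000 trials per setting, center share 0 / 5 / 15%:

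- SE ratio 0.97 / 1.00 / 1.05.
- Opposite verdicts 4.9 / 7.5 / 10.4% at a difference of 1.0, and 2.2 / 3.4 / 4.0% under no effect.
- Type I error 0.054 to 0.066, with a Monte Carlo SE of 0.007.

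**5. Separate run on a center-SD scale.** Week 4 only, no baseline covariate, 3000 trials. The variance share is center SD² / 5.5225.

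| Center SD (share) | SE slope / SE factor | Power slope / factor |
|---|---|---|
| 0 (0%) | 0.354 / 0.363 | 80% / 78% |
| 0.5 (4.5%) | 0.354 / 0.356 | 81% / 80% |
| 0.8 (11.6%) | 0.352 / 0.342 | 80% / 83% |
| 1.2 (26.1%) | 0.348 / 0.313 | 82% / 88% |

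**6. Side check on the ESTIMATE statements.** Three treatments by four weeks need 12 interaction coefficients. The 4% statement has 12. In the text available here the 8% statement has 11, so its final 1 falls on 8% at week 3 and the contrast is not estimable. With one more zero before that 1, it is estimable. A zero may have been lost when the PDF was read.

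**The case against.** The best defence is that the printed programs are sketches. One input dataset name serves three different data layouts (SAP 6.2.2, 6.2.3 and 6.3.2), and some SAS names are misspelled. Production code has to be written from the prose, which is clear and agrees with the pooling rule and the two other programs. The slip would also show in routine output review, because PROC MIXED lists the CLASS variables and the degrees of freedom of each effect.

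Much of this stands. The intended model is not in doubt, the consequence depends on an unstated coding, and a careful reviewer would probably catch it. What does not follow is that the code can stay as it is. The imputation and sensitivity programs are introduced only as code that may be used, while the primary program is given without that reservation. No section says that prose overrides code, and under either coding the program does not fit the model described.

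The size should also be read with care. At zero center variance the unintended model has slightly more power (0.801 against 0.780). More than half of the 9.1% discordance (5.3 / 9.1 = 58%) is present with no center effect at all. The type I error of 0.066 in the smaller simulation is (0.066 − 0.05) / 0.007 = 2.3 Monte Carlo SEs above 0.05; the larger single-week simulation shows no such excess.

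The ESTIMATE count cannot be held against the plan, since the text may have been damaged in reading. It would not harm the reported result in any case: the SAP requires differences "between each active group and the placebo group for the change from baseline to weeks 1, 2, 3 and 4", and the least-squares means statement supplies them, including 8% against placebo at week 4.

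**Conclusion.** The concern holds as a minor error. The mismatch between text and program is certain from the SAP itself. Its consequence is conditional: a wrong model without an error message if center is numeric, a failed run if it is character.

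Within the assumed 0 to 15% center share, the error changes the standard error by −3% to +5%. Power is 0.80 to 0.81 as programmed, against 0.78 to 0.83 as intended. The treatment estimate is not biased, because center labels are unrelated to randomized treatment on average. Opposite verdicts occur in about 5 to 10% of trials at a true difference of 1.0 and about 2 to 4% under no effect; the lower ends (5% and 2%) are the noise of 14 degrees of freedom against 1. A larger center variance would cost more: at a center SD of 1.2 the SE ratio is 0.348 / 0.313 = 1.11. Endpoint, estimand and sample size do not change.

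**What to change.** Before unblinding, change the CLASS line in SAP 6.2.2 to `Class treatment center week patient;`, and do the same wherever that program is reused for the secondary repeated-measures analyses. Treatment still precedes week, so the order of the ESTIMATE coefficients is unchanged.

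Separately, compare the 8% ESTIMATE statement with the source file, and add a 0 before the final 1 only if it is missing there.

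The cost is one word and one look at a file, with no effect on design, sample size or data collection.
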